### **3.3.2. Exclusion Criteria**

Potential participants must **not** meet any of the following exclusion criteria:

1. Abnormal Glucose Tolerance or Diabetes
  - a. Fasting plasma glucose  $\geq$  110 mg/dL (6.1 mmol/L), or
  - b. 2 hour plasma glucose  $\geq$  140 mg/dL (7.8 mmol/L), or
  - c. 30, 60, or 90 minute plasma glucose during OGTT  $\geq$  200 mg/dL (11.1 mmol/L)
2. History of treatment with insulin or other diabetes therapies.
3. Ongoing use of medications known to influence glucose tolerance, e.g. glucocorticoids, growth hormone, anticonvulsants, thiazide or potassium-depleting diuretics, beta adrenergic blockers, niacin and antipsychotics. Participants on such medications should be changed to a suitable alternative, if available, by their primary care provider, and will become eligible one month after medication is discontinued.
4. Ongoing or anticipated future use of any medications known to impact T1D progression or have untoward interactions with hydroxychloroquine, as described in section 7.2.4.
5. Known hypersensitivity to 4-aminoquinoline compounds.
6. G6PD deficiency.
7. History of retinopathy.
8. Active infection at time of randomization.
9. Serologic evidence of current or past HIV, Hepatitis B (positive for Hepatitis B core antibody or surface antigen), or Hepatitis C infection.

10. Deemed unlikely or unable to comply with the protocol or have any complicating medical issues, including prolonged QT interval, a disease previously or likely in the future to require immunosuppression, or abnormal clinical laboratory results that interfere with study conduct or cause increased risk.
11. Be pregnant or breastfeeding.

### **3.4. Enrollment**

Potential study participants will be identified through the ongoing TrialNet Pathway to Prevention Study. Autoantibody-positive individuals in that study are then further evaluated with the performance of OGTTs, additional blood tests, detailed medical history, and physical exam. The results of these evaluations will be used to determine eligibility for this protocol.

### **3.5. Description of Study Cohorts**

While enrollment for the TrialNet Abatacept Prevention Trial (TN18) is open, enrollment in this study for individuals age 6 or older will be limited to those with mIAA confirmed within 6 months of enrollment as one of their two or more autoantibodies. However, those who are age 3-5 years or who reside in countries not participating in TN18 and have normal glucose tolerance and two or more autoantibodies (regardless of mIAA status) are eligible. Otherwise, after completion of enrollment for TN18, all individuals  $\geq 3$  years of age with normal glucose tolerance and two or more autoantibodies regardless of mIAA status are eligible to screen for this study.

### **3.6. Description of Treatment Groups**

The intervention will only be administered to those who provide informed consent to participate. Participants will be randomized to receive either oral hydroxychloroquine or placebo along with close monitoring for abnormal glucose tolerance or diabetes. Blood and serum samples for the primary and secondary outcome determinations will be sent to the Core Laboratories for analysis. Clinical laboratory studies may be done at the local sites.

Participants will be randomly assigned in a 2:1 ratio to treatment arms within strata defined by two stratification factors: prior treatment for T1D prevention (prior enrollment in a prevention study and treatment with placebo vs. prior enrollment in a prevention study and treatment with active therapy vs. no prior enrollment in a prevention study) and age group (<8 years old vs. 8 years old or older).

### **3.7. Treatment Assignment**

After participants (or parents/legal guardians as applicable) sign the consent form, complete the screening visit(s), and meet all of the inclusion criteria and none of the exclusion criteria, they will be randomized to receive either hydroxychloroquine or placebo; each treatment arm will include close monitoring for study endpoints.

#### **3.7.1. Procedures for Unmasking**

Emergency unmasking occurs as follows: Investigators can break the treatment code by contacting the TrialNet Central Pharmacy via the 24-hour emergency number. No approval or intervention by the study sponsor or TrialNet administration is required in emergency situations. The TrialNet Chair, NIDDK TrialNet program officer and TrialNet Medical Monitor will be notified of the unmasking within 24 hours of its occurrence. Non-emergent unmasking will occur upon notification of the TNCC and approval by TrialNet Chair or NIDDK TrialNet program officer. If unmasking is approved, the study sponsor and appropriate TrialNet committees (e.g. Safety Monitoring) will be notified of the event as soon as reasonably possible; however, they will not be unmasked.

### **3.8. Study Assessments**

During the course of the study, participants will undergo frequent assessments of their glucose tolerance status, insulin production, immunologic status, and overall health and well-being (see Schedule of Assessments).

Samples will be drawn for storage in the National Institute for Diabetes and Digestive and Kidney Disease (NIDDK) Repository and at TrialNet Laboratory Sites for future analysis related to T1D.

### **3.9. Study Timeline**

#### **3.9.1. Study Duration**

The study has been designed to provide 83% power to detect a 50% risk reduction in the progression from Stage 1 to Stage 2 or 3 T1D using a two-sided test at the 0.05 level after six years of study duration (approximately 4 years of accrual and a minimum of 2 years of follow-up on all subjects). A total of approximately 201 participants will be allocated in a 2:1 ratio to the two groups.

The assumptions underlying the sample size are: 1) 40% two-year event rate in the placebo group for the progression from Stage 1 to Stage 2 or 3 T1D, 2) detectable hazard ratio of 0.50 (i.e., reducing the hazard rate by 50%, which here translates to 40% vs. 22.5% in the two-year event rates) in the hydroxychloroquine group, 3) a 10% or less dropout rate for a minimum of 2 years of follow-up on all participants in both groups, and 4) assumption that the distribution of time to T1D stage progression is approximately exponentially distributed. Under the above assumptions, the total target number of events that would trigger the final analysis is 80; i.e., the final analysis will be conducted once 80 events (abnormal glucose tolerance or diabetes) have been observed. If the accrual rate is 50 patients per year, with the above assumptions it is estimated that the enrollment period will last approximately 4 years, with a total study duration of approximately 6 years to provide a sufficient number of events to detect the powered detectable difference.

#### **3.9.2. Follow-up Studies**

Participants who have progressed to Stage 2 T1D (confirmed abnormal glucose tolerance) will have reached the primary study endpoint. These participants who have developed abnormal glucose tolerance but have not progressed to Stage 3 T1D (clinical onset) will have the option to remain in this study without further therapy, undergoing close monitoring and safety assessments until the development of Stage 3 T1D (clinically overt diabetes) or until they enroll in another clinical trial, whichever comes first.

Once participants reach Stage 3 (diagnosis of clinical diabetes), they will no longer be followed in the context of this protocol; however, they will be offered follow-up in the Long Term Investigative Follow-Up in TrialNet (LIFT) Study (TN16). Alternatively, individuals who progress to Stage 3 may be eligible for interventional studies sponsored by TrialNet or other organizations under separate INDs. In the event that a participant wishes to participate in another investigational study whose entry criteria exclude participants who have previously received immunomodulating therapy and is otherwise eligible for the new study, the participant may request and be told of their treatment group assignment for the hydroxychloroquine prevention study. Every attempt will be made to minimize the potential bias that this may introduce. The TNCC will make treatment assignment information available to the site investigator of the new study after the participant is determined to be willing to participate and not otherwise excluded from the new study. Other study group members will not be informed of the treatment assignment information. Mitigation of bias issues must be balanced against safety and interests of participants.

## **4. PATIENT MANAGEMENT**

### **4.1. Screening Visit and Eligibility Assessment**

This study will draw participants from the TrialNet Pathway to Prevention Study.

The initial testing for islet autoantibodies, HLA type, and OGTT will generally be done as part of Pathway to Prevention Study. Potential participants in the hydroxychloroquine prevention trial are those with two or more autoantibodies present on two separate samples. Initially, for those age 6 or older, enrollment will require the presence of mIAA antibodies unless the individual resides in a country not participating in the Abatacept Prevention Trial (TN18). After completion of enrollment for the Abatacept Prevention Trial (TN18), any two confirmed autoantibodies will meet criteria for this study. The autoantibodies that may be confirmed are mIAA, GAD65Ab, IA-2/ICA512Ab, ZnT8Ab, and/or ICA. The confirmation of two positive autoantibodies must occur within the six months prior to study drug administration, but the confirmation does not have to involve the same two autoantibodies.

Those individuals with two diabetes-related autoantibodies will then be eligible for additional screening tests and possible enrollment into the hydroxychloroquine prevention trial. A participant must have a normal OGTT (done either as part of the Pathway to Prevention Study or during screening for the hydroxychloroquine prevention trial) within 7 weeks (52 days) prior to randomization. If a participant has a previous abnormal glucose tolerance, he/she must have two consecutive OGTTs with normal glucose tolerance in order to be eligible.

Appendix 1 summarizes the flow of participants from the Pathway to Prevention Study into the hydroxychloroquine prevention trial.

## **4.2. Hydroxychloroquine Trial for At-risk Participants Screening Visit**

Prior to the initial visit, the hydroxychloroquine prevention trial will be described to the potential participant. The participant/parent/guardian will be asked to sign an informed consent document, and minors will be asked to sign an age appropriate assent document, describing the purpose, risks, and benefits of screening for the trial. A participant's signature indicates that he/she understands the potential risks and benefits of study participation. During these visits, clinical tests will be done to determine eligibility.

Any antibody positive relative either not eligible or not willing to be randomized into the hydroxychloroquine prevention trial is eligible for continued follow-up as part of the TrialNet Pathway to Prevention Study.

## **4.3. Randomization and Baseline visits**

Participants will be randomized to either the treatment arm or the placebo arm. Randomization must occur within 7 weeks of a normal OGTT in order to ensure that participants have normal glucose tolerance, and study drug administration must occur within 4 weeks after randomization.

## **4.4. Close Monitoring**

During the study period, all participants will receive close monitoring for development of abnormal glucose tolerance and diabetes. OGTT tests will be performed at approximately six-month intervals thereafter. At each visit, participants will be asked questions about the presence or absence of symptoms associated with diabetes. If participants respond affirmatively or have other laboratory or clinical evidence of disease progression, further evaluation will be performed. Individuals in both of the study arms will have laboratory and mechanistic studies performed as detailed in the Schedule of Assessments.

## **4.5. Administration of Hydroxychloroquine**

The hydroxychloroquine used in these human trials is a 4-aminoquinoline compound (hydroxychloroquine sulfate) supplied as a 200mg tablet for oral administration. As described below, these tablets will be prepared in 100mg increments and over encapsulated for this trial.

Hydroxychloroquine must be stored below 25°C/77°F.

### **4.5.1. Dosing and Dose Withholding**

The target dose is 5 mg/kg/day (actual body weight), up to a maximum of 400mg/day, of hydroxychloroquine or placebo. The dose was chosen based on demonstrated safety and efficacy in other human autoimmune diseases. Dose by body weight will be calculated in 100mg increments and will be equivalent to  $\leq 5$  mg/kg/day averaged over a one-week period.

#### Dose Withholding

1. Study drug will be withheld in those with 3 or more days of fever  $>101^{\circ}\text{F}$  ( $38.3^{\circ}\text{C}$ ) until resolved.
2. If needed, in individuals who have gastrointestinal or other symptoms limiting their tolerance of study medication, the dose may be temporarily reduced at the discretion of the investigator in consultation with the medical monitor.
3. Any abnormal ophthalmologic examination finding possibly related to study medication, confirmed by repeat measure and central reading within 4 months, will result in stopping the study medication (permanently).
4. Grade 2 anemia or thrombocytopenia, i.e. hemoglobin  $<10$  gm/dl and platelets  $<75,000/\text{mm}^3$ . In consultation with the medical monitor, study medication may be restarted after resolution of the Grade 2 anemia or thrombocytopenia. The complete blood count (CBC) will be repeated no more than one month after restarting study medication. If the abnormality recurs, then medication will be discontinued permanently.
5. Study medication should be withheld if a participant develops an adverse event of severe intensity (grade 3 or higher) or a serious adverse event at least possibly related to study medication

Individuals who are unable to continue on study medication due to adverse effects will remain on study and continue with study visits.

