#### **4.5.2. Interruption of Enrollment/Trial Cessation**

Section 4.5.1 describes the circumstances for potential withholding or reduction of drug treatment in individual patients. This section lists events that will necessitate interruption of enrollment in the trial as a whole, pending DSMB review. As part of their ongoing safety review, the DSMB will make independent judgments regarding other adverse events requiring trial interruption.

1. Any death that occurs in the study which is assessed as possibly, probably, or definitely related to study treatment regimen by the study site investigator and the medical monitor.
2. Two or more of the first 10 treated participants or  $\geq 20\%$  of all treated participants experience a clinically significant, drug-related adverse event, resulting in the permanent discontinuation of study treatment.
3. If more than one of the first 10 treated participants or  $\geq 10\%$  of all treated participants develop clinically significant retinal changes, the study will be placed on hold pending review by DSMB.

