## 6. ADVERSE EVENT REPORTING AND SAFETY MONITORING

### 6.1. Adverse Event Definition

#### 6.1.1. Adverse Event

In this clinical trial, an adverse event (AE) is any occurrence or worsening of an undesirable or unintended sign, symptom or disease, whether or not related to the treatment and study procedures.

Throughout the study, the investigator must maintain source documentation of all adverse events. Events *not related to diabetes onset* which are Grade 2 or greater per the NCI CTCAE (see Section 6.1.5. Grading Event Severity below) must be reported to TNCC. The investigator should treat participants with adverse events appropriately and observe them at suitable intervals until the events resolve or stabilize.

Adverse events may be discovered through:

- observation of the participant;
- questioning the participant;
- unsolicited complaint by the participant.

Questioning of the participant should be conducted in an objective manner.

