### Ophthalmologic:

The most important adverse effect of hydroxychloroquine is retinal toxicity. In a retrospective case-control study of 2,361 individuals who had taken hydroxychloroquine for at least 5 years, retinopathy was seen in 7.5% of users when assessed with spectral domain optical coherence tomography and 10 degree standard automated perimetry visual fields; as duration of use increases, an unknown, but

higher percentage that varies with the daily dose was seen. The risk of retinopathy was duration- and dose-dependent, and was less than 2% within 10 years in those taking 4-5 mg/kg/day. There is negligible risk when duration of therapy <6 months and it is unlikely to occur if dose is <5 mg/kg/day actual body weight (generally equivalent to 6.5 mg/kg/day ideal body weight) up to 400 mg/day. Moreover, retinopathy detected by these sensitive techniques is not equivalent to clinically apparent or significant visual effects. Despite longstanding use of hydroxychloroquine for malaria therapy in very young children, there is a dearth of information about retinopathy, suggesting its rarity. Current practice recommendation by the American Academy of Ophthalmology is annual examination after 5 years of drug exposure in those on daily doses  $\leq 5.0$  mg/kg with no major risk factors.

Dermatologic AEs (pruritus, allergic rashes, and increased skin pigmentation), neuromuscular AEs (muscle aches), and insomnia each occur 1% of the time and resolve within 1-2 weeks with continued therapy.

Cardiovascular: Hydroxychloroquine has the potential to cause QT prolongation and should not be administered with other drugs that have a potential effect on the QT interval (*see Drugs Interactions; section 7.2.4.2*). In addition, rare cases of cardiomyopathy have been reported in those over age 50 who received high doses of hydroxychloroquine over a long duration.

Thrombocytopenia and hemolysis are rare and are probably associated with high doses, other drugs, or G6PD deficiency.

There are case reports of allergic reactions (urticarial, angioedema), abnormal liver function tests, and skeletal muscle myopathy, which are reversible over time.

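### Dose-withholding item 4 names anemia or thrombocytopenia as its trigger but joins the two numeric limits with 'and', which leaves room for a less protective reading

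*Protocol*

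**What the plan says.** Item 4 of the Dose Withholding list in Protocol Section 4.5.1 opens with "Grade 2 anemia or thrombocytopenia, i.e. hemoglobin $<10$ gm/dl and platelets" below 75,000/mm3. This opening is a fragment with no verb; the instruction to withhold comes from the list heading.

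The item continues with three rules:
- After consultation with the medical monitor, "study medication may be restarted after resolution of the Grade 2 anemia or thrombocytopenia".
- The blood count is repeated within one month of restarting.
- "If the abnormality recurs, then medication will be discontinued permanently".

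Item 5 of the same list withholds drug for "an adverse event of severe intensity (grade 3 or higher) or a serious adverse event at least possibly related to study medication". The list closes by saying that "Individuals who are unable to continue on study medication due to adverse effects will remain on study and continue with study visits".

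Neither the rest of the protocol nor the SAP restates the two hematologic limits.

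**The concern.** The abbreviation 'i.e.' announces a restatement of what precedes it. Here a trigger built on 'or' is restated with 'and'. A site that goes straight to the numbers could conclude that hemoglobin and platelets must both be below their limits before drug is stopped. An isolated Grade 2 anemia or an isolated Grade 2 thrombocytopenia would then call for no action under item 4.

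This is an operative safety threshold in a multicenter trial that enrols children from age 3 (Protocol Section 3.3.1), and every site should draw the same instruction from the same blood count. Later steps in item 4 depend on the first one: restart, repeat count and permanent discontinuation on recurrence. A permanent discontinuation can in turn count toward the enrollment-interruption rule in Protocol Section 4.5.2, item 2, which concerns a "clinically significant, drug-related adverse event, resulting in the permanent discontinuation of study treatment".

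**Working it through.** The plan gives no figure to reproduce here, and no sample size, event count or alpha bears on the point. The check compares wording and works through the logic.

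**Step 1. Signals within item 4.**

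| Part of item 4 | Wording | Points to |
|---|---|---|
| Trigger phrase | anemia 'or' thrombocytopenia | either one |
| Limits after 'i.e.' | hemoglobin limit 'and' platelet limit | both, unless read as a respective list |
| Restart sentence | anemia 'or' thrombocytopenia | either one |
| Recurrence sentence | 'the abnormality', singular | either one |

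Three of the four parts point to either condition. The fourth agrees with them only if 'and' is read as listing one limit per named condition.

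**Step 2. Where the two readings differ.** Let A be hemoglobin below 10 gm/dl and B be platelets below 75,000/mm3.

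| A met | B met | 'Either' reading | 'Both' reading |
|---|---|---|---|
| no | no | continue | continue |
| yes | no | withhold | continue |
| no | yes | withhold | continue |
| yes | yes | withhold | withhold |

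The readings agree in two states and differ in the other two, which are the isolated cytopenias.

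**Step 3. Does any other rule cover those two states?**
- Item 5 of the same list starts at grade 3 or at a serious event, so a non-serious Grade 2 cytopenia falls outside it.
- Item 2 of the list, and the matching text in Protocol Section 7.3, allow dose changes at the investigator's discretion for symptoms or poor tolerance. An asymptomatic laboratory finding does not clearly fall under either.
- Protocol Section 6.1.1 requires investigators to treat participants with adverse events appropriately and to "observe them at suitable intervals until the events resolve or stabilize". It does not say to stop drug.
- Protocol Sections 6.1.1, 6.2 and 10.3 send events of Grade 2 or above to the coordinating center, and Section 10.3 has the medical monitor review all adverse event reports. These steps make a missed case more likely to be noticed, but none of them orders withholding.

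Item 4 is therefore the only rule that requires withholding for an isolated, non-serious Grade 2 cytopenia.

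**Step 4. How often could it matter?** Protocol Section 7.2 states that "Thrombocytopenia and hemolysis are rare and are probably associated with high doses, other drugs, or G6PD deficiency", and Section 7.3 screens out G6PD deficiency. The documents give no rate for either isolated state, so the two-of-four count in Step 2 describes the logic and is not a frequency.

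**The case against.** The strongest reply is that item 4 is already clear in context. Two conditions are named and two limits follow in the same order, which is an ordinary respective list. The 'both' reading would define anemia partly by a platelet count and would leave the 'or' in the trigger with nothing to do. The trigger also carries a grade, and Protocol Section 6.1.5 supplies a grading system, so a site that records a Grade 2 anemia has met the words of the trigger whatever follows. Adverse event reporting and the medical monitor's review then make a silent misapplication less likely.

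Most of this stands. The respective list is the natural reading and 'either' is evidently what was meant. A reader might infer more: that the protocol requires both cytopenias before drug is withheld, or that participants are being kept on drug when they should not be. The documents support neither inference. The trigger, the restart sentence and the recurrence sentence all run against the first, and nothing shows that any site applies the 'both' reading.

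What the reply does not remove is the conflict between the trigger and the limits meant to restate it. Nothing outside item 4 settles that conflict, and the reporting safeguards do not tell a site to withhold.

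**Conclusion.** The point holds as a minor drafting inconsistency in a safety rule. Item 4 means that either cytopenia triggers withholding, but its limits are joined in a way that permits a less protective reading for an isolated, non-serious Grade 2 event. The readings differ in two of four combinations of the limits.

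No number of affected participants and no delay in withholding can be given, because the documents report no rates beyond calling thrombocytopenia and hemolysis rare. Power, type I error and the primary analysis are unaffected. The conclusion assumes that no site instruction outside the protocol and SAP already settles the wording.

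**What to change.** Replace the first sentence of item 4 with: *Study drug will be withheld for Grade 2 anemia (hemoglobin <10 gm/dl) or Grade 2 thrombocytopenia (platelets <75,000/mm3).* Leave the thresholds and the restart, repeat-count and recurrence sentences unchanged. The new sentence also supplies the missing verb.

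The cost is one sentence, with no added scheduled tests or visits. The Protocol Preface allows revised pages or a supplemental memorandum; if the change is issued as an amendment, Section 9.1 requires review-board approval before it takes effect. It could go into the next planned revision.

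If sites already act on either cytopenia, practice does not change. If any site required both, the fix would add some temporary withholdings, a repeat count within one month of each restart and, on recurrence, some permanent discontinuations. Those judged drug-related and clinically significant would count toward Section 4.5.2, item 2 (two or more of the first 10 treated, or at least 20% of all treated). Affected participants stay on study and, under Protocol Section 8, in the intention-to-treat analysis.
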